- China is far away, making trial monitoring difficult, and this site has no experience in conducting chemoprevention trials. We are highly respectful of these facts and their implications. Therefore, the plan is to implement a very small pilot trial. A main goal is to demonstrate the feasibility of implementing a DCP study at this site. The Northwestern consortium and [name] in particular, has an established track record of successfully working with sites and investigators who are new to the field of cancer chemoprevention. As such, [name] has successfully brought new investigators into the field, which is widely deemed as critically important for the field. He now aims to do so for China, similarly deemed as important. Extensive monitoring of the site will be conducted. It will be monitored on site four times per year by [name] (two times he will be accompanied by a Northwestern-based study monitor). [name] has extensive interactions with China, and [name] (consortium co-PI) was trained as a physician in China, frequently travels there, has conducted several trials in China, and has successfully shipped clinical samples from China to the US. Finally, tissue endpoint biomarkers will be analyzed in China, and will then undergo complete re-analysis in the US by a GI pathologist, [name], thus providing rigorous quality control (QC). [name] is a US trained and practicing physician/scientist, whose research focuses upon colon carcinogenesis and its modulation by chemoprevention agents. Further, as a native born Chinese, he is well poised to ensure communication and QC in the realm of tissue processing.
- A minor issue was raised about the currently unpopular nature of investigating natural products for cancer prevention, and the fact that Berberine is a natural product. In this regard, it is important to consider that many non-natural products have also failed in cancer chemoprevention trials. Further, the majority of all FDA approved small molecule drugs are in fact natural products or directly inspired by them¹⁰⁵. Specifically, for FDA approved small molecule drugs for cancer between 1/1981 and 12/2010, eighty percent were natural products or directly inspired by them. The fact is there is a large body of preliminary data related to Berberine to support its investigation for colorectal cancer, and there is a need for novel agents for exactly this purpose. Finally, a major asset of China is its rich source of bioactive agents. Such natural products have transformed the treatment of such unlikely diseases as acute promyelocytic anemia, where the Chinese natural product arsenic trioxide is now in widespread clinical use in the US⁷⁵.

3. SUMMARY OF STUDY PLAN

This is a single center, double-blind, randomized, placebo-controlled, pilot study. The goal of this Phase I trial is to determine the safety of Berberine in subjects with UC in clinical remission and maintained with Mesalamine. Pilot information about Berberine's ability to modulate relevant biomarkers at the dose being assessed will also be gathered.

Subjects will be randomized in a double-blind fashion to 300 mg TID Berberine (12 subjects) versus placebo (4 subjects), for 3 months. Two additional participants are anticipated to be accrued (for a total of 18 subjects) to account for an anticipated dropout rate of 10%. In order to keep the numbers in either treatment group as planned, dropouts in either treatment group will be replaced by subjects assigned to that same treatment and gender group. Assuming an accrual rate of approximately 1.5 per month, we expect the study to be completed in 12 months.

Subjects will be enrolled and followed up at Department of Gastroenterology, Xijing Hospital, Xi'an, China. For those subjects experiencing grade 2 toxicity felt to be due to Berberine, the dosage will be successively decreased by 100 mg decrements per dose until resolution (note, given TID dosing, this translates to 300 mg/day decrements). Those not tolerating 300 mg/day, will be removed from study, as will those experiencing grade 3 or 4 toxicity at any dose. Compliance will be assessed by pill counts and diary reviews at monthly clinical visits and by measuring plasma Berberine concentrations at the end of the trial. Subjects whose compliance is below 80% will be removed from study.

Colorectal biopsies and blood samples will be taken at the initial visit (pre-treatment). At the end of the 3-month treatment, subjects will repeat earlier screening assessments to determine the outcomes of the primary and secondary objectives. One month post study, subjects will be contacted by clinical visit to assess symptoms.

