5.7 Adherence/Compliance

- 5.7.1 If less than 80% of the dose has been consumed during the study period, the subject will be considered non-compliant. All participants that receive a study agent for any period of time will be evaluable for efficacy and toxicity. Participants will not be replaced.
- 5.7.2 Clinical visits will be made each month to monitor compliance. Pill counts will be performed and patient diary will be reviewed at each clinical visit. Drug levels will be measured in blood on the last day of administration.

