8.3 Off-Agent Criteria

Participants may stop taking study agent for the following reasons: completed the protocol-prescribed intervention, adverse event or serious adverse event, inadequate agent supply, noncompliance, concomitant medications, or medical contraindication. Participants will continue to be followed, if possible, for safety reasons and in order to collect endpoint data according to the schedule of events. Subjects who stop treatment for toxicity reason will be followed until the issue is resolved or stabilized. If the drop-out rate is higher than expected, we will recruit more participants. Participants will not be replaced.

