13.2 Randomization/Stratification

Patients will be randomized by the study statistician. 12 subjects will receive treatment with Berberine and 4 subjects will receive the placebo, in a randomized, double-blinded manner and stratified by gender. Two additional participants are anticipated to be accrued (for a total of 18 subjects) to account for an anticipated dropout rate of 10%. In order to keep the numbers in either treatment group as planned, dropouts in either treatment group will be replaced by subjects assigned to that same treatment and gender group. The ratio of men to women in each treatment group (Berberine/placebo) will be 1:1. The randomization list will be provided by the study statistician to the Investigational pharmacist at Xijing Hospital. Only the Northwestern CRO Quality Assurance Monitors, statistician, and the research pharmacist at Xijing Hospital will know which patient is receiving which treatment.

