13.6 Reporting and Exclusions

Compliance will be formally assessed by clinical visit and pill counts each month, and by measuring blood drug concentrations at the end of the study. Patients will be considered compliant if they have taken 80% of their study agent doses as directed. During the first month of study, patients will be counseled regarding the importance of taking all doses, but will not be removed from the study for missing doses, unless 10 consecutive days are missed. Patients who are found to be non-compliant at the monthly assessments will be kept in the study; their information will be used in the final ‘intent to treat’ analysis, which will contain all randomized patients.

We expect that of 18 recruited participants, all will have complete data; it is possible that up to 10% of participants drop out. Participants will not be replaced. Analysis will be based upon complete data.

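### Section 3 removes subjects below 80% compliance from the study, while 13.6 keeps them for an intent-to-treat analysis and 8.3 follows them off agent; early removal forfeits the only scheduled post-baseline chemistry

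*Combined protocol and SAP*

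**What the plan says.** Section 3 describes monthly pill counts and diary reviews, and then states: "Subjects whose compliance is below 80% will be removed from study". It does not say whether the 80% is judged at each visit or over the whole 90 days.

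Section 13.6 deals with the same subjects: "Patients who are found to be non-compliant at the monthly assessments will be kept in the study". Their data go into an intent-to-treat analysis "which will contain all randomized patients". For the first month it adds that patients "will not be removed from the study for missing doses, unless 10 consecutive days are missed". It closes with: "Participants will not be replaced. Analysis will be based upon complete data".

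Section 8.3 lists noncompliance among the reasons for stopping agent and continues: "Participants will continue to be followed, if possible, for safety reasons and in order to collect endpoint data according to the schedule of events". Section 5.7.1 defines non-compliance as less than 80% of the dose over the study period, but then says: "All participants that receive a study agent for any period of time will be evaluable for efficacy and toxicity". Section 13.7 evaluates all participants for toxicity to day 120. Section 13.8 assesses response despite major deviations. The off-study list in 8.4 does not name noncompliance.

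On replacement, Section 13.2 says "dropouts in either treatment group will be replaced by subjects assigned to that same treatment and gender group", and Section 3 makes the same promise. Sections 5.7.1, 8.3 and 13.6 say there is none.

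**The concern.** Sections 3 and 13.6 give opposite instructions for the same subject. Sections 8.3 and 8.4 separate going off agent from going off study, so if Section 3 meant only the former, it uses the wrong term.

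In a safety trial the difference matters because missed doses can themselves signal poor tolerability. The diary in Appendix D asks for new symptoms and reasons for missed doses in the same field, and Section 6.2 reports discontinuations for abdominal pain, rash or constipation. A rule that drops poor compliers can therefore leave a set selected for tolerating the drug. Depending on when it is applied, it can also lose the organ-toxicity laboratory data that Section 8.1 makes part of the primary endpoint.

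**Working it through.** **The plan's own figures.** Section 13.4 gives zero-event 95% upper bounds from 3/(n+1): 3/17 = 0.176 for all 16 subjects and 3/13 = 0.231 for the 12 on berberine. Both match the stated 0.18 and 0.23. The exact one-sided bounds, 1 − 0.05^(1/n), are 0.171 and 0.221. The recruitment total also reproduces: 16/(1 − 0.10) = 17.8, rounded up to 18. No stated figure is wrong; the question is who counts in n.

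**What early removal loses.** From the visit lists:

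| Visit | Section | Clinical laboratory tests |
|---|---|---|
| Screening | 7.2 | Yes |
| Days 0, 7, 30, 60 | 7.3 | None |
| Day 90 | 7.4 | Yes |
| Day 120 | 7.5 | None |

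In the Section 7.1 schedule, Early Termination shares the Day 120 column. A subject removed before Day 90 therefore has no scheduled chemistry after baseline. The post-treatment UCDAI, research bloods and biopsies also fall at Day 90.

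**Size per subject, if not replaced.** Berberine: 1/12 = 8.3% of the arm's Day 90 data. Placebo: 1/4 = 25%.

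If k berberine subjects lack Day 90 chemistry and no toxicity is seen, the bound for chemistry-detected toxicity becomes 3/(12 − k + 1):

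| k (assumed) | Rule of Three | Exact |
|---|---|---|
| 0 | 3/13 = 0.231 | 0.221 |
| 1 | 3/12 = 0.250 | 0.238 |
| 2 | 3/11 = 0.273 | 0.259 |
| 3 | 3/10 = 0.300 | 0.283 |
| 4 | 3/9 = 0.333 | 0.312 |

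The documents give no non-compliance rate, so k is purely illustrative.

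**How far the rules diverge in month one.** Assume three doses a day, a visit at exactly Day 30, whole days missed, and Section 3 applied at that pill count. By Day 30, 90 doses are due and 80% is 72, so a subject falls below the threshold at 71 or fewer taken, that is 19 or more missed. Section 13.6 removes only after 10 consecutive days, or 30 doses. Over 90 days, 270 doses are due and 80% is 216.

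| Consecutive days missed in month one | At Day 30 | At Day 90 if fully adherent afterwards | Section 3 at Day 30 | Section 13.6 |
|---|---|---|---|---|
| 7 | 69/90 = 77% | 249/270 = 92% | Remove | Keep |
| 9 | 63/90 = 70% | 243/270 = 90% | Remove | Keep |
| 10 | 60/90 = 67% | 240/270 = 89% | Remove | Removal trigger met |

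All three subjects finish compliant under the study-period definition in 5.7.1. The last row shows that 13.6 also has a problem: its own trigger can remove someone who ends at 89%.

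**The case against.** The strongest reply is that Section 3 is a summary and the detailed sections already settle the matter: 13.6 addresses this exact case, names the analysis set, and is supported by 8.3. The protocol also uses removal loosely. Section 3 applies the same phrase to grade 3 or 4 toxicity, yet 8.3 follows subjects who stop for toxicity. Read that way, Day 90 tests would still be sought. That is probably the intent, but Section 3 gives an unqualified instruction, nothing in the documents says later sections prevail, and Section 2.3 acknowledges that the site has not run chemoprevention trials before.

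Second, 5.7.1 measures compliance over the study period, which suggests an end assessment that would lose little data. The timing is indeed unclear. Even so, dropping someone at the end on compliance is a post-randomization exclusion that 13.6 rules out.

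Third, Section 3 itself promises replacement, so the 1/12 and 1/4 losses, and the wider bounds, require removal under Section 3 together with non-replacement under 13.6. This stands as a limit on the numbers. Replacement restores the count but not the subject, and the resulting set is still selected for compliance.

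Fourth, the conflict with 5.7.1 is weaker than that with 13.6, because being evaluable concerns analysis rather than retention; a removed subject could still be evaluated on adverse events. The effect on the primary endpoint is also partial: 13.4 frames it as grade 2 toxicity, events up to removal still count, and 7.5 assesses adverse events 30 days after the last dose. Finally, 8.4 has broad categories, such as protocol violation, that could cover removal. These points narrow the consequence but do not remove the contradiction.

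**Conclusion.** The concern holds. Sections 3 and 13.6 cannot both be followed, and the Section 3 rule is the one that damages the analysis. It should be corrected.

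The consequence depends on timing. Applied before Day 90, and read literally as ending participation, the rule forfeits the only scheduled post-baseline chemistry and the other Day 90 endpoints. Applied at the end, it excludes randomized subjects on a post-randomization variable. The per-subject losses above assume no replacement, and the month-one comparison assumes the rule is applied at Day 30. The overall effect cannot be quantified without a non-compliance rate. The intent-to-treat analysis stated in 13.6 is sound.

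**What to change.** Replace the Section 3 sentence with wording such as: *Participants who take less than 80% of their doses stay in the study, are followed for safety and Day 90 assessments where possible even if they stop agent (Section 8.3), and are analysed as randomized.*

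In 13.6, make two changes:

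- Turn the first-month trigger of 10 consecutive missed days into a reason to stop agent, not to leave the study.
- State that basing the analysis on complete data does not take any dosed subject out of the toxicity count.

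Once non-compliers stay in, they are not dropouts and replacement does not arise on this ground. The wider disagreement on replacement (3 and 13.2 against 5.7.1, 8.3 and 13.6) still needs one answer.

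Two options are worth considering. Day 90 laboratory results in someone who stopped earlier are off-treatment, so the chemistry panel could also be drawn at the visit where agent is stopped. Section 5.7.1 could define compliance as tablets taken over tablets prescribed at the dose in force.

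The core change is one sentence and two phrases, with no new mandatory visit or test. It does need the amendment route in Section 14.3 (DCP, then IRB and Ethics Committee), so it is best bundled with other edits. The optional draw is 12–16 ml, at the Day 90 volume, per subject who stops early; the 5.7.1 wording adds no procedure.

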4. PARTICIPANT SELECTION

4.1 Inclusion Criteria

- 4.1.1 Patients with ulcerative colitis in clinical remission (UCDAI, Appendix A) ≤ 1 for at least 3 months), regardless of how long ago they were diagnosed for UC.
- 4.1.2 Receiving maintenance therapy with Mesalamine for at least 3 months.
- 4.1.3 Age 18 - 70 years. Because no dosing or adverse event data are currently available on the use of Berberine in participants <18 years of age, children are excluded from this study but will be eligible for future pediatric trials, if applicable.
- 4.1.4 ECOG performance status ≤ 1 (Karnofsky $\geq 70\%$; see Appendix C).
- 4.1.5 Participants must have normal organ and marrow function as defined below:

Leukocytes	$\geq 3,000/\text{microliter}$
Absolute neutrophil count	$\geq 1,500/\text{microliter}$
Platelets	$\geq 100,000/\text{microliter}$
Total bilirubin	within normal institutional limits. Higher values ($\leq 3 \times$ institutional upper limit of normal (ULN)) are acceptable in participants with: 1. known or suspected cholangitis associated with Crohn's disease, or 2, known or suspected inborn errors of metabolism that lead to increased bilirubin.
AST (SGOT)/ALT (SGPT)	$\leq 1.5 \times$ institutional ULN
Creatinine	within normal institutional limits
- 4.1.6 Women of child-bearing potential and men must agree to use adequate contraception (hormonal or barrier method of birth control; abstinence) prior to study entry and for the duration of study participation, due to unknown, but potential risk of Berberine causing uterine contractions and miscarriage³⁷. Should a woman become pregnant or suspect she is pregnant while participating in this study, she should inform her study physician immediately.
- 4.1.7 Ability to read, understand, and the willingness to sign a written informed consent document.

4.2 Exclusion Criteria

- 4.2.1 Participants who have had any immunomodulatory treatment in the past 3 months will be excluded.
- 4.2.2 Participants who have taken any medicines that are inducers, inhibitors or substrates of select CYP isozymes (see Appendix B) within the past 3 months will be excluded. Participants who have consumed either grapefruit juice or Seville orange juice in the past 7 days will be excluded.
- 4.2.3 Participants with Dysplasia-associated mass or lesion (DALM) due to longstanding idiopathic inflammatory bowel disease will be excluded.
- 4.2.4 Participants who are currently receiving any other investigational agents or have received investigational agents within the past 3 months will be excluded.
- 4.2.5 Participants with a history of allergic reactions attributed to compounds of similar chemical or biologic composition to Berberine will be excluded.
- 4.2.6 Patients with uncontrolled intercurrent illness including, but not limited to, ongoing or active infection, symptomatic congestive heart failure, unstable angina pectoris, cardiac arrhythmia, or psychiatric illness/social situations that in the opinion of investigators would jeopardize patient safety of data integrity are excluded. Individuals who are HIV positive will not necessarily be excluded, will be considered on a case-by-case basis, but will be required to meet criteria related to patient safety and data integrity, as assessed by investigators.
- 4.2.7 Pregnant women are excluded from this study because Berberine has a potential for causing uterine contractions and miscarriage³⁷ because there is an unknown but potential risk for adverse events in nursing infants secondary to treatment of the mother with Berberine, breastfeeding should be discontinued if the mother is treated with Berberine. Women are considered to be of child-bearing potential if they are not surgically sterile or under the age 65 and have menstruated within the last two years.

4.3 Inclusion of Women and Minorities

Both men and women and members of all races and ethnic groups are eligible for this trial.

4.4 Recruitment and Retention Plan

Xijing Hospital of Digestive Diseases is solely dedicated to diseases of the gastrointestinal system. Annually, the hospital serves over 150,000 outpatients and over 6000 inpatients, performs over 20,000 endoscopic examinations with over 6000 being colonoscopies. Xijing Hospital of Digestive Diseases has established track records for Inflammatory Bowel Disease patients who are being followed-up. Thus potentially eligible subjects can be identified and contacted prior to the procedure. In addition, advertisements will be posted at Xijing Hospital of Digestive Diseases with study contact information. Adequate minority participation will be ensured with our patient population.

Once identified, eligible patients will be contacted by the study coordinator who will explain the details of the study and the requirements for participation. Patients who are interested in the trial will be given a copy of the IRB approved consent form. After the patient signs the consent form, the patient will then be monitored by the research coordinator. The coordinator will be the main contact for patients in accordance with the protocol to ensure pleasant clinic visits. Participant retention will be maximized by frequent patient contact. During each telephone contact and/or clinical visit, patients will be assessed for adverse events and counseled on AE management and the use of rescue medication. Compliance will be assessed by pill counts and diary reviews at monthly clinical visit, and by measuring plasma Berberine concentration at the end of the trial.

Northwestern University will work closely with Xijing Hospital of Digestive Diseases on an ongoing basis to monitor recruitment and adjust or employ new strategies as needed to maximize patient recruitment with an emphasis on ensuring a balanced representation of women and men. This assistance will include coordinating recruitment material design and placement.

Participants will not be reimbursed for participation, but all of their clinical test cost will be covered, including the Mesalamine that will be taken during the trial periods.

5. AGENT ADMINISTRATION

Intervention will be administered on an outpatient basis. The initial treatment will be 300 mg TID; if this is not tolerated, the dosage will be decreased by 100 mg/dose (300mg/day) until a tolerable dosage is reached. Reported adverse events (AEs) and potential risks are described in Section 6.2.

5.1 Dose Regimen and Dose Groups

16 participants will be randomized into one of two groups: 12 participants will receive 300 mg Berberine three times per day; 4 participants will receive placebo tablets three times per day. Two additional participants (for a total of 18 participants) are anticipated to be enrolled to account for an anticipated dropout rate of 10%. In order to keep the numbers in either treatment group as planned (3:1), dropouts in either treatment group will be replaced by subjects assigned to that same treatment and gender group. Dosing will extend for 90 days.

5.2 Berberine Administration

Participants will take 300 mg three times per day (3 x 100 mg tablets, three times a day) of Berberine for a period of 90 days. Participants should take tablets within one hour after a meal with water every 6-8 hours. Patients will be asked to return to the clinic within 6 days of the initial screening visit to pick up the study medication. If patients are unavailable to return to the clinic within this timeframe to pick up the study medication, the study medication may be shipped to the participant's home. Three (3) bottles (each containing 120 tablets) will be distributed initially and 3 bottles will be distributed at the Day 30 and Day 60 visits. An additional bottle may be dispensed if needed.

